9.6.2 Statistical Methods for Safety Analyses

Safety and tolerability will be assessed by clinical review of all relevant parameters separately for adults and pediatric participants including AEs and postvaccination temperature measurements.

The analysis strategy of safety parameters is summarized in Table 6. The proportion of participants with solicited injection-site AEs (redness/erythema, swelling, tenderness/pain from Day 1 to Day 5 postvaccination for adult participants, and redness/erythema, swelling, tenderness/pain, and hard lump from Day 1 to Day 14 postvaccination for pediatric participants) and solicited systemic AEs (muscle pain/myalgia, joint pain/arthritis, headache, and tiredness/fatigue from Day 1 to Day 14 postvaccination for adult participants, and muscle pain/myalgia, joint pain/arthritis, headache, tiredness/fatigue, and hives and

welts for pediatric participants) will be provided along with the corresponding within-group 95% CIs (based on the exact binomial method proposed by Clopper and Pearson [Clopper, C. J. and Pearson, E. S. 1934]). In addition, the broad AE categories consisting of the proportion of participants with any AE, a vaccine-related AE, a SAE, an AE which is both vaccine-related and serious, discontinuation due to an AE, and the proportion of participants who died will be summarized in the same manner separately for adult and pediatric participants. The proportion of participants with maximum temperature measurements meeting the Brighton Collaboration cut points (from Day 1 through Day 5 postvaccination for adult participants, and Day 1 through Day 7 for pediatric participants) will also will be provided along with the corresponding within-group 95% CIs. Point estimates by vaccination group will be provided for all other safety parameters (specific AE terms and system organ class terms).

The analysis of safety parameters will be evaluated separately for adult and pediatric participants at 3 separate time points: (1) following administration of any of the 3 doses of V114 and Pevnar 13™ (combined across each of the vaccinations), (2) following administration of PNEUMOVAX™23 (administered 12 months after allo-HSCT), and (3) following administration of a 4th dose of V114 or Pevnar 13™ (administered 12 months after allo-HSCT). Descriptive summaries of AEs following administration of any of the 3 doses of V114 or Pevnar 13™ will include NSAE within 14 days of vaccination and SAEs/special events of interest occurring Day 1 through Month 12 after allo-HSCT (prior to vaccination with PNEUMOVAX™23 or a 4th dose of V114 or Pevnar 13™). Descriptive summaries of AEs following administration of PNEUMOVAX™ will include NSAEs within 14 days of vaccination and SAEs/special events of interest occurring Month 12 after allo-HSCT (Day 1 relative to vaccination with PNEUMOVAX™23) through Month 13 after allo-HSCT (Day 30 relative to vaccination with PNEUMOVAX™23). Descriptive summaries of AEs following administration of a 4th dose of V114 or Pevnar 13™ will include NSAEs within 14 days of vaccination and SAEs/special events of interest occurring Month 12 after allo-HSCT (Day 1 relative to vaccination with a 4th dose of V114 or Pevnar 13™) through Month 13 after allo-HSCT (Day 30 relative to vaccination with a 4th dose of V114 or Pevnar 13™).

The rate of SAEs, vaccine-related SAEs and death that occur throughout the entire study follow-up period will also be summarized per 1000 person-years of follow-up by vaccination group.

In addition, the proportion of participants who have new onset and/or worsening of GVHD as well as relapse and progression of the underlying disease (ie, the disease for which the allo-HSCT was performed [see inclusion criterion 2 in Section 5.1]) during study participation will be summarized descriptively. Limited summaries may also be generated following each of the 3 doses of vaccination of V114 or Pevnar 13™.

Safety analyses will be based on observed data (ie, no imputation of missing data).

Table 6 Analysis Strategy for Safety Parameters

Safety Endpoint	95% CI for Within-Group Comparison	Descriptive Statistics
Injection-site redness/erythema (Days 1 to 5 for adult participants and Day 1 to Day 14 for pediatric participants) [†]	X	X
Injection-site swelling (Days 1 to 5 for adult participants and Day 1 to Day 14 for pediatric participants) [†]	X	X
Injection-site tenderness/pain (Days 1 to 5 for adult participants and Day 1 to Day 14 for pediatric participants) [†]	X	X
Injection-site hard lump/induration for pediatric participants (Days 1 to 14) [†]	X	X
Muscle pain/myalgia (Days 1 to 14) [†]	X	X
Joint pain/arthralgia (Days 1 to 14) [†]	X	X
Headache (Days 1 to 14) [†]	X	X
Tiredness/fatigue (Days 1 to 14) [†]	X	X
Hives or welts/urticarial for pediatric participants (Days 1 to 14) [†]	X	X
Any AE [‡]	X	X
Any vaccine-related AE [‡]	X	X
Any SAE [‡]	X	X
Any vaccine-related SAE [‡]	X	X
Discontinuation due to AE [‡]	X	X
Death [‡]	X	X
Maximum temperature measurements meeting the Brighton Collaboration cut points (Days 1 to 5 for adult participants and Day 1 to Day 7 for pediatric participants)	X	X
Specific AEs by SOCs and PT		X
[†] Includes solicited events only. [‡] These endpoints are broad adverse event categories. For example, descriptive statistics for the safety endpoint of “Any AE” will provide the number and percentage of participants with at least 1 AE. AE = adverse event; CI = confidence interval; PT = preferred term; SAE = serious adverse event; SOC = System Organ Class; X = results will be provided.		

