
 Objective: To evaluate the safety and tolerability of PNEUMOVAX™23 (administered 12 months after allo-HSCT in participants who do not develop GVHD) with respect to the proportion of participants with AEs within each vaccination group. 	
Following vaccination with PNEUMOVAX™23 for adults ≥18 years of age:
 
 Solicited injection-site AEs from Day 1 through Day 5 postvaccination Solicited systemic AEs from Day 1 through Day 14 postvaccination Vaccine-related SAEs from Month 12 after allo- HSCT to 1 month after vaccination or the completion of the study. 
Following vaccination with PNEUMOVAX™23 for pediatrics (3 to <18 years of age):
 
 Solicited injection-site AEs from Day 1 through Day 14 postvaccination Solicited systemic AEs from Day 1 through Day 14 postvaccination Vaccine-related SAEs from Month 12 to after allo-HSCT to 1 month after vaccination or the completion of the study.

 Objective: To evaluate the safety and tolerability of a 4th dose of V114 and a 4th dose of Prevnar 13™ (both administered 12 months after allo-HSCT in participants who develop GVHD) with respect to the proportion of participants with AEs within each vaccination group. 	
Following vaccination with a 4th dose of V114 or Prevnar 13™ for adults ≥18 years of age:
 
 Solicited injection-site AEs from Day 1 through Day 5 postvaccination Solicited systemic AEs from Day 1 through Day 14 postvaccination Vaccine-related SAEs Day 1 through 6 months after 4th vaccination of V114 and Prevnar 13™ or completion of the study. 
Following vaccination with a 4th dose of V114 or Prevnar 13™ for pediatrics (3 to <18 years of age):
 
 Solicited injection-site AEs from Day 1 through Day 14 postvaccination Solicited systemic AEs from Day 1 through Day 14 postvaccination Vaccine-related SAEs from Day 1 through 6 months after 4th vaccination of V114 and Prevnar 13™ or completion of the study.

 Objective: To evaluate the serotype-specific opsonophagocytic activity (OPA) Geometric Mean Titers (GMTs) at 30 days following the 3rd dose of V114 and following the 3rd dose of Prevnar 13™ within each vaccination group. 	
 Serotype-specific OPA responses for the 15 serotypes in V114 at Day 90

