4.4 Beginning and End of Study Definition

The overall study begins when the first participant signs the informed consent/assent form. The overall study ends when the last participant completes the last study-related telephone-call or visit, withdraws from the study, or is lost to follow-up (ie, the participant is unable to be contacted by the investigator).

For purposes of analysis and reporting, the overall study ends when the Sponsor receives the last serology assay result.

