	
 • Proportion of participants with solicited systemic AEs (muscle pain/myalgia, joint pain/arthralgia, headache, tiredness/fatigue, and hives and welts) from Day 1 through Day 14 postvaccination • Proportion of participants with vaccine-related SAEs from Day 1 postvaccination to Month 12 after Allo-HSCT

Key Secondary Endpoints
	
Immunogenicity:
 
 • Serotype-specific OPA GMTs at 30 days following the 3rd dose of V114 or Prevnar 13TM (Day 90) 
Safety: The following analysis endpoints will be evaluated following vaccination with PNEUMOVAXTM23 and following the 4th dose of V114 or Prevnar 13TM (separately) for adults (≥ 18 years of age):
 
 • Proportion of participants with solicited injection-site AEs (redness/erythema, swelling, tenderness/pain) from Day 1 through Day 5 postvaccination • Proportion of participants with solicited systemic AEs (muscle pain/myalgia, joint pain/arthralgia, headache, and tiredness/fatigue) from Day 1 through Day 14 postvaccination • Proportion of participants with vaccine-related SAEs from Month 12 Allo-HSCT to 1 month postvaccination or the completion of the study. (from Month 12 to Month 13 after allo-HSCT or the completion of the study) 
The following analysis endpoints will be evaluated following vaccination with PNEUMOVAXTM23 and following the 4th dose of V114 or Prevnar 13TM (separately) for pediatrics (3 to <18 years of age):
 
 • Proportion of participants with solicited injection-site AEs (redness/erythema, swelling, tenderness/pain, hard lump) from Day 1 through Day 14 postvaccination • Proportion of participants with solicited systemic AEs (muscle pain/myalgia, joint pain/arthralgia, headache, tiredness/fatigue, hives and welts) from Day 1 through Day 14 postvaccination • Proportion of participants with vaccine-related SAEs from Month 12 Allo-HSCT to 1 month postvaccination or the completion of the study. (from Month 12 to Month 13 after allo-HSCT or the completion of the study)

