9.3 Hypotheses/Estimation

Objectives of the study are stated in Section 3. This is an estimation study and no formal hypothesis testing will be performed.

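### Section 9.6.2 stops the 4th-dose SAE summary at Day 30, but Section 3 defines that secondary endpoint through 6 months or study completion, and Section 9.1 does not settle which applies

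*Combined protocol and SAP*

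**What the plan says.** Section 3 gives the two Visit 6 vaccines different SAE windows. For the 4th dose of V114 or Prevnar 13 the adult endpoint is "Vaccine-related SAEs Day 1 through 6 months after 4th vaccination of V114 and Prevnar 13™ or completion of the study", and the pediatric endpoint is "Vaccine-related SAEs from Day 1 through 6 months after 4th vaccination of V114 and Prevnar 13™ or completion of the study". For PNEUMOVAX 23 in adults it is "Vaccine-related SAEs from Month 12 after allo- HSCT to 1 month after vaccination or the completion of the study", and the pediatric line matches. The synopsis repeats all of this.

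The schedule of activities (Section 1.3, footnote d) and Section 8.1.10 place a safety call 6 months after Visit 6, only for participants who received V114 or Prevnar 13 at that visit. Section 8.4.1 has SAEs reported for the whole of each participant's time in the study.

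On the analysis side, Section 9.6.2 sets three analysis time points. For the third, after the 4th dose, it takes SAEs from Month 12 "through Month 13 after allo-HSCT (Day 30 relative to vaccination with a 4th dose of V114" or Prevnar 13. Section 9.1 lists one set of key secondary safety endpoints after PNEUMOVAX 23 "and following the 4th dose of V114 or Prevnar 13TM (separately) for adults", with a matching list for children. Both lists gloss the SAE window as "from Month 12 to Month 13 after allo-HSCT or the completion of the study". Section 9.4.2 and Table 6 give no window for SAEs.

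**The concern.** Two current sections give different end dates for the same named secondary endpoint. Section 9.6.2 is the one a programmer would follow. It plans a proportion with a Clopper-Pearson 95% CI for vaccine-related SAEs, separately for adults and children. With the cut at Day 30, a participant whose first vaccine-related SAE after the 4th dose comes later stays in the denominator and counts as having no event, although Section 3 counts that event.

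The study is estimation only, so the planned estimates are its results. If the conflict stays open until after unblinding, someone will have to choose between two written safety windows with the results in view.

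**Working it through.** There is no sample-size or power figure to reproduce. The check is a comparison of windows, followed by day arithmetic.

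**Windows side by side (vaccine-related SAEs)**

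| Source | After PNEUMOVAX 23 | After 4th dose of V114 or Prevnar 13 |
|---|---|---|
| Section 3 and synopsis | 1 month, or study completion | 6 months, or study completion |
| Section 9.1 | Month 13, or study completion | same shared text |
| Section 9.6.2 | Month 13 (Day 30) | Month 13 (Day 30) |
| Section 9.4.2, Table 6 | none given | none given |
| Last scheduled contact (Section 1.3) | Visit 7, Day 30 to 44 | call, Day 166 to 194 |

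The PNEUMOVAX 23 column is consistent. In the 4th-dose column, Sections 3 and 9.6.2 conflict. Section 9.1 is ambiguous there rather than contradictory. Its shared text follows the PNEUMOVAX 23 endpoint, but for a 4th-dose recipient the last scheduled contact is the 6-month call, so its study-completion clause could reach that far.

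**Follow-up outside the Section 9.6.2 summary**

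Inputs: summary cut at Day 30 (Section 9.6.2); call window Day 166 to 194 and Visit 7 window Day 30 to 44 (Section 1.3). Six months is taken as the midpoint of the call window, (166 + 194)/2 = Day 180.

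Uncovered days = end of endpoint window − end of summary.

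- Nominal: 180 − 30 = 150 days; 150/180 = 83.3%.
- Earliest call: 166 − 30 = 136 days; 136/166 = 81.9%.
- Latest call: 194 − 30 = 164 days; 164/194 = 84.5%.
- If Month 13 is read as the actual Visit 7 date, and that visit is as late as Day 44 with the earliest call: 166 − 44 = 122 days; 122/166 = 73.5%.

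So the gap is 136 to 164 days on the explicit Day 30 cut. Its lower end falls to 122 days on the looser reading of Month 13.

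**Does another planned analysis supply the endpoint?** Section 9.6.2 also reports SAEs, vaccine-related SAEs and deaths per 1000 person-years over all follow-up, by vaccination group. Later events enter there. But those rates pool time after doses 1 to 3, after PNEUMOVAX 23 and after the 4th dose. They do not give the proportion among 4th-dose recipients.

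**The case against.** The strongest reply is that little depends on this. SAEs are collected throughout, later ones enter the person-year rates, nothing is tested, and only one component of one secondary endpoint is touched. Appendix 3 asks for a reasonable temporal sequence before an event is called vaccine-related, so such events may be rare after Day 30, and elapsed time says little about how many would be missed. The supplemental SAP could settle the wording.

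Most of that stands, and it limits the size of the problem. It does not remove the conflict, because the person-year rates are a different quantity in a different set of participants. Section 9 allows changes through a supplemental SAP, but nothing in the documents commits to this one.

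Two supporting texts carry little weight. Section 9.3 ("Objectives of the study are stated in Section 3") refers to objectives, whereas the 6-month window stands among the endpoints. Section 4.4 ("The overall study ends when the last participant completes the last study-related telephone-call or visit") defines the end of the study as a whole, not of one participant's follow-up. The point does not need either: Section 3, the footnote to the schedule and Section 8.1.10 are enough.

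**Conclusion.** The concern holds. Followed as written, Section 9.6.2 yields a 4th-dose proportion and CI for vaccine-related SAEs that are not the endpoint in Section 3. Section 9.1 should be clarified in the same step.

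The size can be stated only in follow-up time: about five sixths of the nominal 6-month window, with Day 180 assumed for 6 months. The effect on the reported proportion cannot be estimated. The solicited AE components, the primary endpoints, the sample size and data collection are unaffected. This should be fixed, but it does not threaten the main results.

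**What to change.** - **Section 9.6.2:** summarise vaccine-related SAEs after the 4th dose (proportion and exact 95% CI, adults and children separately) from Day 1 through 6 months or study completion, as Section 3 states.
- **Section 9.1:** split the shared window. Give PNEUMOVAX 23 to Month 13, and the 4th dose of V114 or Prevnar 13 to 6 months or study completion.
- **Timing:** record the change before unblinding, in the supplemental SAP that Section 9 provides for.

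Optional, and not required by the conflict: use the longer window for all SAEs, deaths and specific events of interest after the 4th dose, and keep a Day 30 column alongside it.

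The cost is wording in two sections and one table window. No new data are needed, because SAE reporting already covers the period and the 6-month call is already scheduled.

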1.3 Schedule of Activities (SoA)

Study Period	Screening	Intervention										Follow-up		Comments
		1	2	Phone Contact	3	Phone Contact	4	Phone Contact	5	Phone Contact	6	Phone Contact	7	
Visit Number:	1	2	Phone Contact	3	Phone Contact	4	Phone Contact	5	Phone Contact	6	Phone Contact	7	Phone Contact ^d	Results from all screening procedures at Visit 1 must be available before randomization into the study at Visit 2 (Day 1), which must occur ≤30 days after Visit 1.
Scheduled Time:		Day 1	Day 15	Day 30	Day 45	Day 60	Day 75	Day 90	9 Months after Allo-HSCT	12 Months after Allo-HSCT	15 days after Visit 6	30 Days after Visit 6	6 Months after Visit 6	
Visit Window:	Within 30 days before Visit 2	90 to 180 days after Allo-HSCT	Day 15 to Day 19 after Visit 2 ^a	Day 30 to Day 44 after Visit 2 ^a	Day 15 to Day 19 after Visit 3 ^b	Day 30 to Day 44 after Visit 3 ^b	Day 15 to Day 19 after Visit 4 ^c	Day 30 to Day 44 after Visit 4 ^c	Day 256 to Day 284 after Allo-HSCT	Day 335 to Day 395 after Allo-HSCT	Day 15 to Day 19 after Visit 6	Day 30 to Day 44 after Visit 6	Day 166 to Day 194 after Visit 6 ^d	
Administrative and General Procedures														
Informed Consent	X													Consent must be obtained before any study procedures.
Informed Consent for Future Biomedical Research (Optional)	X													Consent for future biomedical research samples must be obtained before the blood sample for ≥18 years of age and saliva for <18 years of age (DNA sample) is collected.
Assignment of Screening Number	X													
Inclusion/Exclusion Criteria	X	X												
Medical History	X	X												The participant's medical history for the 5 years prior to these visits will be reviewed. History of tobacco use will also be collected for all participants.

Study Period	Screening	Intervention										Follow-up		Comments
		1	2	Phone Contact	3	Phone Contact	4	Phone Contact	5	Phone Contact	6	Phone Contact	7	
Visit Number:	1	2	Phone Contact	3	Phone Contact	4	Phone Contact	5	Phone Contact	6	Phone Contact	7	Phone Contact ^d	Results from all screening procedures at Visit 1 must be available before randomization into the study at Visit 2 (Day 1), which must occur ≤30 days after Visit 1.
Scheduled Time:		Day 1	Day 15	Day 30	Day 45	Day 60	Day 75	Day 90	9 Months after Allo-HSCT	12 Months after Allo-HSCT	15 days after Visit 6	30 Days after Visit 6	6 Months after Visit 6	

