Visit Window:	Within 30 days before Visit 2	90 to 180 days after Allo-HSCT	Day 15 to Day 19 after Visit 2 ^a	Day 30 to Day 44 after Visit 2 ^a	Day 15 to Day 19 after Visit 3 ^b	Day 30 to Day 44 after Visit 3 ^b	Day 15 to Day 19 after Visit 4 ^c	Day 30 to Day 44 after Visit 4 ^c	Day 256 to Day 284 after Allo-HSCT	Day 335 to Day 395 after Allo-HSCT	Day 15 to Day 19 after Visit 6	Day 30 to Day 44 after Visit 6	Day 166 to Day 194 after Visit 6 ^d	
Future Biomedical Research														
Blood (DNA) for Future Biomedical Research (Optional) for adult participants ≥18 years of age.		X												Collected from randomized participants who provided consent for future biomedical research (Section 8.8)
Saliva (DNA) for Future Biomedical Research for pediatric participants <18 years of age.		X												Collected from randomized participants who provided consent/assent for Future Biomedical Research (See Section 8.8).

^a When scheduling the Phone Contact (Day 15) and Visit 3 (Day 30), “Day 1” is the date of Visit 2 vaccination.
^b When scheduling the Phone Contact (Day 45) and Visit 4 (Day 60), “Day 1” is the date of Visit 3 vaccination.
^c When scheduling the Phone Contact (Day 75) and Visit 5 (Day 90), “Day 1” is the date of Visit 4 vaccination.
^d This Phone Contact (6 months after Visit 6) will only be conducted in recipients of V114 or Prevnar13™ at Visit 6.

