4 STUDY DESIGN

4.1 Overall Design

This is a Phase 3, randomized, double-blind, active comparator-controlled, parallel-group, multicenter, clinical study to describe the safety, tolerability, and immunogenicity of V114 and Prevnar 13™ when administered as a 3-dose regimen in recipients of allo-HSCT.

Prospective participants will be screened for enrollment at Visit 1, which must occur within 30 days before Visit 2 (Day 1). At Visit 2 (Day 1), which must occur 90 to 180 days after a first allo-HSCT, eligible participants will be randomly assigned in a 1:1 ratio to 1 of the 2 blinded study vaccines (V114 or Prevnar 13™).

A total of approximately 250 adult and 50 pediatric participants will be randomized so that approximately 150 participants will receive V114 and approximately 150 participants will receive Prevnar 13™. The randomization process will be performed using stratification techniques to ensure a reasonable balance between the 2 study vaccine groups with regard to the following factors: use of systemic steroids within 14 days before randomization (Day 1),

age category (3 to <18 years and 18 to 49 years or ≥ 50 years), and haploidentical donor status (yes or no).

Blinded study vaccine (V114 or Prevnar 13™) will be administered to each eligible participant at each of the following 3 time points: Visit 2 (Day 1), Visit 3 (Day 30), and Visit 4 (Day 60).

Eligible participants will also receive a single dose of PNEUMOVAX™23 at Visit 6 (12 months after allo-HSCT). However, participants who develop chronic GVHD during the first year after allo-HSCT will be considered ineligible to receive PNEUMOVAX™23 and will instead receive a 4th dose of blinded study vaccine (V114 or Prevnar 13™) at Visit 6.

Participants will be followed for local and systemic AEs from Day 1 through Day 14 following each vaccination. Information for SAEs and deaths, regardless of whether the events are considered to be vaccine-related by the investigator, will be collected from the time consent is signed through completion of participation in the study. An external Data Monitoring Committee (DMC) will conduct a periodic review of safety and tolerability data for the adult V114 Phase 3 program. A description of the structure, function, and guidelines for decision-making by the DMC, along with the timing and content of the safety reviews will be outlined in the DMC charter. Information regarding the composition of the DMC is provided in Appendix 1.

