8.1.10 Telephone Contact Questionnaire

Site personnel will contact study participants or the participant's legally acceptable representative at approximately 9 months after the reported date of their allo-HSCT to collect additional information based on a Telephone Contact Questionnaire provided by the Sponsor. Data to be reported from this discussion will include SAEs, specific events of interest, and/or any updates to previously reported safety information.

If a study site visit occurs within 30 days before the 9-month post-allo-HSCT time point, then this Phone Contact will not occur and the Telephone Contact Questionnaire will not be required.

A second safety follow-up telephone contact will need to be conducted only for those participants receiving a 4th dose of V114 or Prevnar 13™ at 6 months after Visit 6.

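### Section 9.6.2 ends the 4th-dose SAE summary at Day 30 although Section 3 sets the endpoint at 6 months, so later SAEs are counted only in the pooled person-year rate

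*Combined protocol and SAP*

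**What the plan says.** Participants without chronic GVHD receive PNEUMOVAX 23 at Visit 6. Under Section 4.1, "participants who develop chronic GVHD during the first year after allo-HSCT will be considered ineligible to receive PNEUMOVAX™23"; they receive a 4th dose of their blinded conjugate vaccine instead.

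Follow-up then differs by path. Footnote d of the schedule in Section 1.3 states: "This Phone Contact (6 months after Visit 6) will only be conducted in recipients of V114 or Prevnar13™ at Visit 6". Section 8.1.10 repeats the rule: "A second safety follow-up telephone contact will need to be conducted only for those participants receiving a 4th dose". Everyone else finishes at Visit 7, 30 to 44 days after Visit 6. SAEs and deaths are collected until participation ends (Section 4.1).

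The analysis window for the 4th dose is given in four places:
- Section 3, secondary objectives (pediatric wording; the adult endpoint and the synopsis have the same window): "Vaccine-related SAEs from Day 1 through 6 months after 4th vaccination of V114 and Prevnar 13™ or completion of the study".
- Section 9.1: one bullet covers PNEUMOVAX 23 and the 4th dose together and runs from Month 12 to Month 13, or to study completion.
- Section 9.4.2: proportions with an SAE, a vaccine-related SAE and death following the 4th dose, with no end date.
- Section 9.6.2: the 4th-dose summary of SAEs runs from Month 12 to Month 13, defined as "Day 30 relative to vaccination with a 4th dose of V114" or Prevnar 13.

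Section 9.6.2 adds one overall summary, shown by vaccination group: "The rate of SAEs, vaccine-related SAEs and death that occur throughout the entire study follow-up period will also be summarized per 1000 person-years". It is not split by period or by the vaccine given at Visit 6.

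**The concern.** The 6-month contact exists to observe safety after the 4th dose, and Section 3 names an endpoint that uses it. A programmer following 9.6.2 would cut the 4th-dose table at Day 30. The stated secondary endpoint would then have no matching table, and five months of collected data would surface only inside a whole-study rate that does not show when, or on which vaccine path, an event occurred.

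A second feature of that rate also needs care. Follow-up after Visit 6 depends on a post-randomisation event, chronic GVHD, so 4th-dose recipients supply more person-time than their share of participants.

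**Working it through.** **1. Where would an SAE on, say, Day 100 after the 4th dose be counted under 9.6.2?**
- Summary after the first three doses: no, it stops at Month 12.
- PNEUMOVAX 23 summary: no, different participants.
- 4th-dose summary: no, it stops at Day 30.
- GVHD and relapse summary over all participation: only if the event is one of those, and then not as an SAE.
- Whole-study person-year rate: yes.

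**2. Person-time.** The plan gives no expected SAE rate, person-years or chronic-GVHD share, so there is no planned figure to reproduce. Inputs from the schedule in Section 1.3: Day 1 falls "90 to 180 days after Allo-HSCT" (midpoint 135); Visit 6 is nominally day 365 (window 335 to 395); the last visit on the PNEUMOVAX 23 path is 30 days after Visit 6 (window 30 to 44); the last contact on the 4th-dose path is 180 days after Visit 6 (window 166 to 194).
- PNEUMOVAX 23 path: A = 365 − 135 + 30 = 260 days.
- 4th-dose path: B = 365 − 135 + 180 = 410 days; B/A = 1.58 (1.49 with Day 1 at day 90, 1.70 at day 180).

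Assumptions: a share f of 10% to 50% receives a 4th dose; deaths and dropout are ignored.

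**3. Dilution of the late window.** Day 31 to Month 6 is 150 days, so its share of person-time is 150f / [fB + (1 − f)A].
- f = 30%: 45 / (123 + 182) = 45/305 = 14.8%.
- Lowest (f = 10%, Day 1 at day 90): 15/320 = 4.7%.
- Highest (f = 50%, Day 1 at day 180): 75/290 = 25.9%.

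With otherwise equal rates and f = 30%, doubling the SAE rate in this window raises the whole-study rate by only 14.8%.

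**4. Weight of 4th-dose recipients in the pooled rate.** Their share of person-time is w = fB / [fB + (1 − f)A]. At f = 30%, w = 123/305 = 40%. After Visit 6 alone it is 54/(54 + 21) = 72%.

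Let R be the event-rate ratio, chronic GVHD to others, constant over time. Relative to equal follow-up, the pooled rate is multiplied by [wR + (1 − w)] / [fR + (1 − f)]. At f = 30%:

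| R | Change in pooled rate |
|---|---|
| 1 | 0% |
| 1.5 | +4.5% |
| 2 | +7.9% |
| 3 | +12.9% |

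Over f = 10% to 50% and Day 1 at day 90, 135 or 180, the change is 2.0% to 15.1% for R = 1.5 to 3.

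**5. The direction is not fixed.** Keep f = 30% and R = 2 in the common period, so its rate is 0.7 × 1 + 0.3 × 2 = 1.30 (others = 1). Suppose the chronic-GVHD rate has fallen to 1.0 in the late window. The pooled rate is (260 × 1.30 + 45 × 1.0)/305 = 383/305 = 1.256, which is 3.4% below 1.30.

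**6. Between arms.** With the same f in both arms the ratio stays 1.00. With f = 25% against 35% and R = 2:
- pooled: (456/312.5)/(400/297.5) = 1.085;
- equal follow-up: 1.35/1.25 = 1.080.

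**The case against.** The best defence is that this is a conflict between sections and not a missing analysis. Section 3 states the 6-month endpoint, 9.1 allows study completion as an alternative end, and 9.4.2 sets no Day 30 limit, so the study team could produce the 6-month table anyway. That is fair, but 9.6.2 is the section that defines the tables, its cut-off is explicit, and nothing says which section prevails.

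The defence of the person-year rate is stronger:
- Dividing by person-years is a usual way to handle unequal follow-up, and this rate is a descriptive extra in a study without hypothesis tests.
- The Day 1 to Month 12 proportions and the separate Month 12 to 13 proportions, all with exact confidence intervals, are unaffected by unequal follow-up.
- A 13% shift equals a Poisson 95% half-width, 1.96/√N, only at N = (1.96/0.13)² ≈ 227 events per arm. With about 150 participants per arm, deaths cannot reach that number.

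All of this stands.

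Two stronger readings are tempting. A reader might infer that the pooled rate hides late SAEs. It does the opposite: it is the one SAE summary in 9.6.2 that counts them, though diluted; the Day 30 cut-off is what leaves them out of the 4th-dose summary. A reader might also infer that the rate is biased upward because participants with chronic GVHD are sicker. Section 8.4.8 does have new or worsening GVHD reported as an AE, which makes a higher rate plausible, but the documents give no SAE rate by GVHD status, and step 5 shows that the sign can reverse.

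**Conclusion.** The inconsistency is established by the text alone: a 6-month endpoint in Section 3, a Day 30 cut-off in 9.6.2 and an ambiguous window in 9.1. If 9.6.2 is followed, SAEs from Day 31 to Month 6 after the 4th dose have no separate summary. How far they are diluted in the pooled rate depends on the assumed 4th-dose share.

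The unequal weighting is real but secondary. Its effect on the rate depends on a rate ratio and a time course that the documents do not supply, and it moves the between-arm ratio by about 0.005 in the example. It supports an added line in the table; it does not support calling the planned rate wrong.

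**What to change.** Before unblinding, in the protocol or in the supplemental SAP that Section 9 provides for:
1. Reconcile the 4th-dose SAE window in 9.1 and 9.6.2 with the 6-month endpoint in Section 3.
2. Report SAEs, vaccine-related SAEs and deaths from the 4th dose through 6 months by vaccination group, as proportions with the exact interval already planned and as person-year rates.
3. Show the person-year rate for the common period, Day 1 to 30 days after Visit 6, next to the all-follow-up rate.

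The cost is a few table rows and a sentence or two of text; the 6-month contact is already scheduled, so no new data are needed. The common-period rate will contain fewer events: it rests on 150 × 260/365.25 = 106.8 person-years per group. The late window adds 45 × 150/365.25 = 18.5 person-years per group at a 30% share (6.2 to 30.8 for 10% to 50%), so its rate will be imprecise. The common-period rate should stand beside the 6-month 4th-dose summary and not replace it, because on its own it would drop the late events altogether.
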